#### **11.4 Nasopharyngeal swabs**

Nasopharyngeal swabs will be taken for viral quantification by quantitative PCR on:

- Screening: If a potential study participant has already been identified as COVID-19-positive from an outside testing facility, as per current institutional protocol, a nasopharyngeal swab will be obtained for quantitative PCR. Study drug therapy will be initiated within 3 days of screening, including on the same day of screening.
- Each day of treatment (Day 1 and Day 3 (+ 1 day)).
- Follow-up Visits on Days 7 and 14

Testing for SARS-CoV-2 will be done upfront and residual samples will be tested for baseline viral load. If there's a problem in supplies, repeat sampling at the indicated time points may not be feasible and will not be considered a protocol deviation.

All samples will be transported to the Molecular Diagnostics facility (Attn: [name]) The screening samples will be tested for SARS-CoV-2 as per current institutional protocol; The residual sample left over from clinical testing, as well as from subsequent testing, will be processed by the Molecular Diagnostics facility and the resulting research analytes will be transported to the [name] laboratory for storage and analysis ([name]).

Any remaining RNA may be also analyzed for the markers of antiviral immunity described in the blood correlative studies.

### **12 WITHDRAWAL OF SUBJECTS**

#### **12.1 Treatment Discontinuation**

Upon treatment discontinuation all end of treatment evaluations and tests will be conducted. All participants who discontinue due to an AE must be followed until the event resolves or stabilizes. Appropriate medical care should be provided until signs and symptoms have abated, stabilized, or until abnormal laboratory findings have returned to acceptable or pre-study limits. The final status of the AE will be reported in the participant's medical records and the appropriate eCRF.

Reasons for treatment discontinuation should be classified as follows:

- Death
- Toxicity: treatment related or unrelated
- Participant non-compliance with study requirements
- Investigator judgment
  - The Investigator may discontinue a participant if, in his/her judgment, it is in the best interest of the participant to do so.
- Participant voluntary withdrawal

## 13 RISKS TO SUBJECTS

### 13.1 Interferon Alpha-2b

Interferon alpha-2b may cause fever, chills and flu-like symptoms; loss of appetite; nausea; vomiting, diarrhea and abdominal pain; fatigue; lowered white blood count may increase risk of infection; lowered platelets may lead to an increase in bruising or bleeding; hair loss. Other risks which may be common in cases of prolonged administration of interferon alpha-2b include drowsiness; temporary confusion; anxiety, amnesia, irritability, confusion, delusions and depression which can be severe; numbness and/or tingling in the hands and/or feet, skin rashes and inflammation of the pancreas. Inflammation of the pancreas is swelling or irritation of the pancreas which may result in tenderness or pain in the stomach and/or back. When the pancreas is inflamed, the body is not able to absorb all the nutrients it needs.

Additional information on risk is included in the Investigator's Brochure or package insert.

### 13.2 Rintatolimod

Clinical experience with rintatolimod totals over 800 patients with more than 400 patients receiving rintatolimod for at least six (6) months, greater than 200 patients for one (1) year, over 50 patients up to two (2) years, and with 20 or more patients over two (2) years at doses as high as 1200 mg i. v. twice weekly. No evidence of dose-limiting organ toxicity, including hematologic, liver, or renal toxicity, has been observed.

Adverse events related to infusion such as mild flu-like symptoms, transient headache, fever, myalgia, arthralgia, and fatigue/malaise which were seen, usually occur during the initial weeks of treatment and tend to subside on repeated administration. These side events were seen in Chronic Fatigue Syndrome patients, cancer patients, chronic hepatitis B infected patients and individuals infected with HIV at doses of 200 and 400 mg and higher. Patients that experience these minor side effects can continue on rintatolimod and as noted, these signs and symptoms typically subside after several weeks of continued treatment. Specific symptoms of note include a flushing reaction, characterized by at least one occurrence of erythema of the face, neck and chest, which has been observed in approximately 10% of patients treated in various studies. Usually the flushing is both mild and transient and disappears with repeated dosing. Occasionally, it can be accompanied by a tightness of the chest, tachycardia, anxiety, shortness of breath, subjective reports of "feeling hot", diaphoresis and nausea. The reaction is usually infusion-rate dependent and can generally be controlled by slowing the infusion rate. An antihistamine (diphenhydramine hydrochloride) can be helpful in controlling and reducing the response in the occasional patient for whom the symptom persists. Other less frequently occurring adverse effects include nausea, diarrhea, itching, urticaria, bronchospasm, transient hypotension, photophobia, rash, bradycardia, and transient visual disturbances. A severe unexpected local reaction to extravasation of rintatolimod (Ampligen®, Poly I:Poly C12U) at the infusion site in the dorsum of the left hand was reported in a Chronic Fatigue Syndrome patient with chilblains. Several patients experienced liver enzyme level elevations while receiving rintatolimod associated with chronic dosing over many weeks.

Rintatolimod has been dosed in combination with alpha interferon in investigator-initiated studies under investigator IND applications during the period between December 1985 and April 1994. A total of 24 patients received combination treatments. Clinical conditions included renal cell carcinoma, chronic myelogenous leukemia, melanoma, and ovarian cancer. Rintatolimod was

Roswell Park Protocol No.: I-659920

given as an IV infusion at a dose of 300 mg twice weekly. The starting dose was sometimes as low as 1-10 mg. The interferons were administered at a dose of 3 million Units daily, with some doses of 0.75 million units at the low side and up to 6 million units at the higher side.

The therapy with rintatolimod in combination with alpha interferon was generally well tolerated without evidence of dose-limiting or cumulative toxicities. The most frequent adverse reactions were considered minor in severity and duration. Most of them were flu-like symptoms such as chills, cold feeling, fatigue, decreased appetite, fever, muscular aches. Also, shortness of breath has been seen as well as hypotension, nausea, anemia, dyspnea, numbness, itching and blurred vision. These adverse events were judged possibly related to the condition of the patients, but also possibly related to the administration of rintatolimod or interferon. In some cases, worsening of the patient's condition has been seen due to tumor progression, but in general favorable clinical patterns were observed in these patients with advanced disease. Such combinations were not intended to be immune modulating and were evaluated in the context of clinical cancer care.

For more risk information, reference the Investigator's Brochure or package insert.

## **14 POTENTIAL BENEFITS TO SUBJECTS**

Patients enrolled in this study may demonstrate improved virus control, manifested by reduced symptoms and improved oxygenation or lack of progression of infection to pneumonia and ARDS.

## **15 DATA AND SPECIMEN BANKING**

All samples for correlative analysis will be sent to the [name] laboratory for processing, storage, and analysis. Samples will be used for planned study assays as well as for future studies that include, but are not limited to, immune responses to viral infections and to immunotherapy.

Any clinical data that is associated with the samples, will be stored on a secure server in the Department of Medicine, will be accessible only by the PI, Co-Investigators and PI designated data manager and, will be password protected. All computer entry and networking programs will be done using PIDs only. Any clinical data and/or specimens for future research will require verification of an IRB-approved protocol and will be de-identified before being released to investigators within and outside of Roswell Park.

**Note:** All investigator or analyzing research laboratories housing research samples need to maintain current Temperature Logs and study-specific Sample Tracking and Shipping Logs. The Principal Investigator/Laboratory Manager must ensure that the stated lab(s) have a process in place to document the receipt/processing/storage/shipping of study-related samples/specimens. This is required for both observational and interventional clinical studies collecting clinical samples.

## **16 MEASUREMENT OF EFFECT**

### **16.1 Primary Endpoints**

- The **primary safety** endpoints are frequency of grade 3 or 4 AEs considered to be possibly, probably, or definitely related to the treatment regimen.
- Evaluate kinetics of viral load in nasopharyngeal swabs based on quantitative PCR in the course of treatment and Days 7, and 14.

## 16.2 Secondary Endpoints

- Clinical efficacy will be assessed by the frequency of these complications: (i) progression of infection requiring hospitalization; (ii) respiratory failure requiring mechanical ventilation (primary efficacy endpoint); and (iii) death within 30 days. If present, acute respiratory distress syndrome (ARDS) will be graded by Berlin criteria (42).
- Kinetics of viral load in the peripheral blood and nasopharyngeal swab based on quantitative PCR in the course of treatment and Days 7 and 14.
- Kinetics of changes of the immune subsets and circulating inflammatory mediators (including CRP, cytokines, chemokines, interferons) in peripheral blood in the course of treatment and at Days 7 and 14.
- Induction of known mediators of antiviral immunity that include (myxovirus resistance gene, MxA; protein Kinase R (PKR); oligoadenylate synthetase-2 (OAS2); RNase-L, IFN-stimulated gene-15 (ISG15); IFN-induced proteins with tetratricopeptide repeats (IFIT1) and IFN-inducible transmembrane protein 3 (IFITM3), TLR3, RIG-I, MDA5, IRF3, IRF7, in nasopharyngeal swabs material and blood cells of patients on all tiers of treatment. Expression of ACE2 (receptor for SARS-CoV-2 entry) and potentially other genes involved in SARS-CoV-2 infection will be tested in nasopharyngeal samples.

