## 2.3 Past experience with IFN $\alpha$ and Rintatolimod

**Interferon-alpha** (INTRON® A) is currently FDA approved for the adjuvant treatment of stage III melanoma. It has been examined by multiple investigators as an immune modulator in the setting of vaccine therapy with demonstrated safety (15). It has been extensively evaluated in the setting of metastatic CRC (as single agent or in combination with chemotherapy or IL-2), but was

Roswell Park Protocol No.: I-659920

shown to be largely ineffective (16-33) at daily doses ranging from 3-20 million units/m^2, administered subcutaneously or intravenously. In the treatment of melanoma, a small study by Astsaturov and colleagues (34) administered IFN $\alpha$ -2b in previously vaccinated melanoma patients, and was shown to convert immunization into objective clinical responses, suggesting its ability to amplify the effectiveness of local T cells infiltration and/or function at the tumor site. Vaishampayan et al. examined IFN $\alpha$ -2b 5 million units subcutaneously three times a week following vaccination with a melanoma vaccine (Melaccine) (35). Treatment at this dose was well tolerated. Similarly Mitchell et al. recently completed a large trial examining IFN $\alpha$ -2b, 5 million units subcutaneously three times a week for one year (36). Di Pucchi and Pilla similarly examined the combination of a melanoma peptide vaccine with IFN $\alpha$ -2b, 3 million units subcutaneously three times a week, with little to no toxicity.

We propose to include a short course of high dose interferon alpha-2b (with the dose-escalation lead-in [0-5-10-20] and with maximum 20 million units/m^2, IV, on Days 1 and 3). The maximum dose of 20 million units/m^2 is similar or lower than the previously evaluated doses in melanoma patients (37-39). In this group of patients, in accordance with previous reports, we expect to consistently observe flu-like symptoms. However, this regimen hasn't been evaluated in patients with respiratory viral infection, and additional AEs may be observed. Specifically, augmentation of innate immune responses may also worsen inflammatory lung injury in patients with COVID-19 infection, and therefore safety and efficacy are primary endpoints of this trial.

**Rintatolimod** (Selective toll-like receptor-3 [TLR3] Ligand; analog of poly IC with reduced toxicity for i. v. use).

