### **Primary Endpoint**

- Evaluate kinetics of viral load expressed as Ct values in nasopharyngeal swab samples over time measured at baseline (day 0), Days 3 (last day of treatment), 7, and 14 (40). The primary endpoint will be the area under the Ct curve (AUC).

The primary Phase IIa safety endpoint is the frequency of grade 3 or 4 AEs considered to be probably or definitely related to the treatment regimen.

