### 19.2.2 Efficacy

In order to compare the AUC between rintatolimod versus historical institutional benchmarks we will use the highly efficient approach proposed by Chandrasekhar et al (48). Ct values measured at baseline (Day 0), Days 3, 7 and 14 will be used to measure the AUC using a standard trapezoidal rule where the AUC for the  $i$ th subject in group  $k$  ( $k=1$  for rintatolimod and  $k=2$  for control) as  $AUC_{jk} = \sum_{i=1}^m c_j Y_{ijk}$  where  $t_1 = 0, t_2 = 3, t_3 = 7, t_4 = 14, t_5 = 30$ ,  $m = 5$ , the  $Y_{ijk}$ 's denote the corresponding Ct values per subject at the respective time points and

$$c_j = \begin{cases} \frac{t_{j+1} - t_j}{2}, & j = 1 \\ \frac{t_j - t_{j-1}}{2}, & j = m \\ \frac{t_{j+1} - t_{j-1}}{2}, & \text{otherwise} \end{cases}$$

If a Ct value is  $>40$  it will be considered right censored for the purpose of this analysis, which corresponds to a non-detectable level. We can re-express this formulation using a linear mixed model with details given exactly as in Chandrasekhar et al. (48). A large AUC value for a respective subject is a measure of treatment efficacy as compared to a subject with a lower AUC

Roswell Park Protocol No.: I-659920

value. The primary test of efficacy will be H0:  $AUC=130$  (log2 copies) x day versus H1:  $AUC>130$  (log2 copies) x day.

The secondary clinical efficacy endpoints of (i) progression of infection requiring hospitalization in patients who were not inpatients at study entry; (ii) respiratory failure requiring mechanical ventilation; and (iii) death within 30 days will be compared using Fisher's exact test. Time to a Ct value of non-detectable will be examined using an exact discrete time-to-event Cox model. The analysis of correlative endpoints will be primarily descriptive and graphical in nature.

The primary test of efficacy will be one-sided and tested at level alpha=0.05. All additional tests will be two-sided and tested at level alpha=0.05.

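### Section 16.2 labels mechanical ventilation the primary efficacy endpoint and nasopharyngeal viral load secondary, against the rest of the protocol; with the override clause in Section 8.2, this leaves room to promote an unpowered clinical result over the Ct AUC

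*Combined protocol and SAP*

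**What the plan says.** Section 16.2 stands under a secondary heading. Its first bullet lists three clinical components, the last two as "ii) respiratory failure requiring mechanical ventilation (primary efficacy endpoint); and (iii) death within 30 days". Its second bullet reads "Kinetics of viral load in the peripheral blood and nasopharyngeal swab based on quantitative PCR in the course of treatment and Days 7 and 14", which makes nasopharyngeal viral load secondary alongside blood viral load.

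Section 16.1, directly above, lists the same variable as primary: "Evaluate kinetics of viral load in nasopharyngeal swabs based on quantitative PCR in the course of treatment and Days 7, and 14". Section 8.1 agrees. For Phase IIa, Section 19.1 is more specific: "The primary endpoint will be the area under the Ct curve (AUC").

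Sections 8.2 and 19.1 list ventilation among the secondary endpoints without any primary label. Section 19.2.2 also calls it secondary and assigns Fisher's exact test. On error levels, Section 19.2.2 says "The primary test of efficacy will be one-sided and tested at level alpha=0.05" and makes every other test two-sided at 0.05.

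Section 8.2 adds a clause that no other section repeats. It concedes that the study is not powered for the clinical endpoint, then says that any clinical element showing a statistical difference between arms will overrule as the efficacy endpoint.

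**The concern.** Section 16 puts one variable in both tiers and attaches a primary label to an item in a secondary list. A protocol should name one primary efficacy endpoint before analysis. This matters more here because Phase IIa is a non-randomised single arm, so naming the endpoint in advance is one of the few protections against choosing it by result.

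On its own, the 16.2 label might pass as leftover text. Section 8.2 makes that harder, because it points the same way: a clinical component that turns out significant is to take precedence over the AUC. An author who wished to lead with a favourable ventilation result could cite both sections. No section sets a testing order or a multiplicity adjustment to prevent it.

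**Working it through.** **The texts side by side**

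| Section | Nasopharyngeal viral load | Mechanical ventilation |
|---|---|---|
| 1.1 / 1.2 | primary objective | clinical efficacy is a secondary objective |
| 8.1 / 8.2 | primary | secondary, but may overrule if significant |
| 16.1 | primary | not listed |
| 16.2 | secondary | secondary heading, primary label |
| 19.1 (Phase IIa) | primary, as Ct AUC | secondary |
| 19.2.2 | one-sided test, 0.05 | secondary; Fisher's exact test, two-sided 0.05 |
| 19.3 | sample size given | none |

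Section 16.2 is the only place where nasopharyngeal viral load is secondary, and the only place where ventilation is called primary. Only the AUC has a hypothesis (130 against a larger value), a one-sided alpha and a sample size. The intended primary is therefore recoverable from Section 19.

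**The plan's own figure.** Section 19.3 states power 0.80 for AUC 144 against 130 with n = 10. Its inputs are SD 6.5 at baseline and 4.5 afterwards, and correlation 0.3. Trapezoidal weights for Days 0, 3, 7 and 14 are 1.5, 3.5, 5.5 and 3.5.
- Weight times SD: 9.75, 15.75, 24.75, 15.75. The sum is 66 and the sum of squares 1203.75.
- Variance = 0.7 × 1203.75 + 0.3 × 66² = 2149.4, so SD = 46.4.
- Power = Φ(14 / (46.4/√10) − 1.645) = 0.245.

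The stated 0.80 does not reproduce. That is a separate matter and does not affect which endpoint was designated. It is used here only to show that the AUC is the one endpoint the plan tried to size.

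**How little n = 10 could say about ventilation (illustration).** Assume a 40% reference rate; Section 8.2 gives this only for ventilation or death combined. Assume true rates of 20% or 10%. This uses a one-sample exact binomial, not the plan's Fisher test.
- At one-sided 0.05, the largest rule is at most 1 event in 10: 0.6¹⁰ + 10 × 0.4 × 0.6⁹ = 0.046. Two events would give 0.167. Power is 0.38 at 20% and 0.74 at 10%.
- With 0.025 in the favourable tail, as a two-sided 0.05 test allows, only 0 events qualifies: 0.6¹⁰ = 0.006. Power is 0.11 at 20% and 0.35 at 10%.

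**The override clause (illustration).** If efficacy may be claimed on the AUC or on any of three clinical components, each at 0.05 without adjustment, the nominal error is 1 − 0.95⁴ = 0.185 under independence. This is an upper figure: it counts both directions for the two-sided tests, exact tests are conservative, and the components overlap. It cannot be made exact, because the clause refers to a difference between arms while Phase IIa has one arm, and Section 19.2.2 names no comparator for the clinical tests.

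**The case against.** The strongest reply is that Section 19 governs the analysis and leaves no doubt. It calls the AUC primary and the clinical components secondary. The heading of 16.2 itself says secondary, and the parenthesis may mean only that ventilation leads the three clinical items. This largely stands: the label is an outlier, and the documents do not support reading it as a rival primary endpoint.

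A reader might go further and infer that ventilation could be tested one-sided at 0.05, doubling its favourable-tail error from 0.025, or that two primary tests give 1 − 0.95² = 9.75% false-positive error. The documents do not support either. Section 19.2.2 ties the one-sided level to the AUC hypothesis, and the same section classes ventilation as secondary. Section 16.2 supplies no test, alpha or sidedness. These figures describe no procedure in the plan.

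A reader might also count the remark in Section 2.3, repeated in 2.2, "and therefore safety and efficacy are primary endpoints of this trial", as further conflict. It is compatible with a primary AUC: Section 9 speaks of antiviral efficacy, Section 19.2.2 calls the AUC test the primary test of efficacy, and neither background section names ventilation.

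What the reply does not answer is Section 8.2. Section 19 neither repeats nor withdraws the override clause, so the classification in Section 19 does not close that route.

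**Conclusion.** The point holds as a contradiction in current endpoint text. Section 16.2 mislabels ventilation and misplaces nasopharyngeal viral load; Sections 8.1, 16.1 and 19.1 contradict it on viral load, and Sections 8.2, 19.1 and 19.2.2 on ventilation. The intended primary efficacy endpoint for Phase IIa is the Ct AUC.

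The harm is limited but real. Together with the override clause, the label gives textual grounds for putting an unpowered clinical result above the AUC after the data are seen, with no multiplicity control. The conclusion rests on comparing the sections, not on a number. The binomial powers depend on an assumed 40% ventilation rate and assumed true rates. The 0.185 is a nominal upper figure under independence.

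**What to change.** 1. In Section 16.2, delete the parenthetical primary label after the ventilation item, and remove the nasopharyngeal swab from the secondary viral-load bullet so that it covers peripheral blood only.
2. In Section 8.2, delete the sentence that lets a significant clinical element overrule. Without this step the edits to 16.2 leave the main route open, and a statement that the AUC is the sole primary would itself conflict with 8.2.
3. In Sections 8, 16 and 19, add one statement: *The nasopharyngeal Ct AUC is the only primary efficacy endpoint of Phase IIa. Hospitalisation, mechanical ventilation and death within 30 days are secondary and are tested two-sided at 0.05.* The sidedness is what Section 19.2.2 already prescribes.
4. Optionally, for clarity, say in Sections 2.2 and 2.3 that the efficacy meant is nasopharyngeal viral load.

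The cost is one wording amendment. Sample size, alpha, tests and data collection stay as they are. It should be done before the efficacy data are analysed.

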## 17 SAFETY EVALUATION

### 17.1 Adverse Events

An adverse event or adverse experience (AE) is any untoward medical occurrence associated with the use of a drug in humans, whether or not considered drug related. Therefore, an AE can be ANY unfavorable and unintended sign (including an abnormal laboratory finding), symptom, or disease temporally associated with the use of a medicinal (investigational) product, whether or not considered related to the medicinal (investigational) product (attribution of ‘unrelated’, ‘unlikely’, ‘possible’, ‘probable’, or ‘definite’).

An AE is considered “unexpected” if it is not listed in the investigator brochure or is not listed at the specificity or severity that has been observed; or if an investigator brochure is not required or available, is not consistent with the risk information described in the general investigational plan in other study-related documents.

